4.3.2.2.1 Lower limb amputation

Frequency tables of patients with LLA (see [Section 4.1.1.1](#)) by treatment, SOC and PT will be provided. In addition incidence rates will be displayed.

Kaplan Meier analyses (cumulative incidence functions) for time to first LLA will be provided by treatment and stratified by study if feasible. Cumulative proportion of patients and the number of patients "at risk" will be provided.

The number of LLA episodes per patients will be summarized in a frequency table. Additionally a listing of patients with recurrent events will be provided.

For SAF-M2 the following analyses will be performed additionally:

- Frequencies of reasons leading to the LLA
- Number of LLA episodes per patient
- Number of LLA episodes per patient excluding those due to trauma and tumor
- Level of amputation for the first LLA, excluding amputation due to trauma and tumor (highest)
- Number of patients having a major LLA as first LLA
- Number of patients with any major LLA
- Number of patients having a knee or above knee LLA as first LLA
- Number of patients with any knee or above knee LLA

Descriptive statistics will be provided to summarize all amputation events occurring after the first LLA event.

4.3.2.2.2 Adverse events related to amputation

The types of analyses to be performed on these events are outlined in [Table 4.3:1](#). The analyses will be performed for these events based on all treated patients and in the subgroup of patients with a subsequent amputation, but for events before the actual amputation only. Events occurring after the first amputation will not be included.

Frequency tables of patients with events preceding amputations (see [Section 4.1.1.2](#)) by treatment, group of PT as specified in Appendix 6.1, SOC and PT will be provided. In addition incidence rates will be displayed.

Kaplan Meier analyses (cumulative incidence functions) for time to first event will be provided by treatment and stratified by study; hereby the analysis will not be provided on individual PT level but events being grouped into vascular AEs, diabetic foot related AEs, wound/infections or nervous system disorders and volume depletion (see [Appendix 6.1](#)). Cumulative proportion of patients and the number of patients "at risk" will be provided. In addition, Cox regression analyses will be performed for the above defined AE groups if sample size is statistically sufficient, i.e. if at least 14 patients with events in total over the 2 treatment groups have been reported.

A listing of AEs with onset during any other than randomized treatment will be provided.

AEs related to amputations occurring after the first amputation event will be analysed using descriptive statistics and will be provided in the final report.

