## **8. RESEARCH QUESTION AND OBJECTIVES**

The primary objective of this exploratory meta-analysis is to evaluate the frequencies, incidence rates, and hazard ratios of lower-limb amputation (LLA) events (primary outcome) and of AEs related to amputation (secondary outcome) in patients treated with empagliflozin compared with placebo in the pooled population of the long-term studies 1245.25, 1245.110, and 1245.121 (SAF-M1), in the pooled population of studies 1245.110 and 1245.121 (SAF-M2), and in each of the 3 studies separately.

The exploratory objectives are to evaluate the frequencies of recurrent LLA events and of AEs related to recurrent LLA events and to assess the frequencies and incidence rates of patients with AEs related to amputation preceding the amputation for empagliflozin compared with placebo in SAF-M1, SAF-M2, and in each of the 3 studies separately. Further exploratory objectives are to evaluate the frequencies, incidence rates, and hazard ratios of the primary and secondary outcomes by subgroup and of the secondary outcome by grouped PTs for SAF-M1 and SAF-M2 as well as to assess details on LLA events for SAF-M2 in patients treated with empagliflozin compared with placebo.

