Disposition, demographics, exposure	Yes	Yes	Yes	Yes	Yes
Concomitant diagnoses and therapies	Yes	Yes	Yes	Yes	Yes
Lower limb amputation					
Frequencies	Yes	Yes	Yes	Yes	Yes
Incidence rates	Yes	Yes	Yes	Yes	Yes
Time to onset analyses	Yes	Yes	Yes	Yes	Yes
Time to onset analyses with competing risk	Yes	-	-	-	-
Sensitivity analyses (heterogeneity analyses, forest plot)	Yes	Yes	-	-	-
Adverse events related to amputations (definition based on list of PTs)					
All patients					
Frequencies	Yes	Yes	Yes	Yes	Yes
Incidence rates	Yes	Yes	Yes	Yes	Yes
Time to onset analyses	Yes	Yes	Yes	Yes	Yes
Patients with amputations only, i.e. preceding events					
Frequencies	Yes	Yes	Yes	Yes	Yes
Incidence rates	Yes	Yes	Yes	Yes	Yes
Time to onset analyses (KM only)	Yes	Yes	Yes	Yes	Yes
Lower limb amputation events occurring after the first LLA event					
Descriptive Statistics (Frequency tables with absolute and relative frequencies)	Yes	Yes	Yes	Yes	Yes
Adverse Events related to amputations occurring after the first LLA event					
Descriptive Statistics (Frequency tables with absolute and relative frequencies)	Yes	Yes	Yes	Yes	Yes

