##### *AEs related to amputation*

Subgroup analyses for SAF-M1 and SAF-M2 will be carried out.

For AEs related to amputation, analyses for different grouped events will be performed (see the SAP [[c16853237](#), Appendix 6.1]). Cumulative proportions of patients and the number of patients at risk will be provided. In addition, Cox regression analyses will be performed for vascular AEs, diabetic-foot-related AEs, wound/infection, nervous system disorders, and

volume depletion events if the sample size is statistically sufficient, i.e. at least 14 patients with events in total over the 2 treatment groups have been reported.

An ITT approach will be used as a secondary analysis, which includes all events during the observation period after starting randomised treatment, regardless if the patient was taking study medication or not when the event occurred.

A listing of AEs with onset during any treatment other than the randomised treatment will be provided.

Additionally, AEs related to amputation preceding the amputation will be summarised for patients with amputation; AEs with onset after the amputation will not be considered in the analysis of this sub-population.

AEs related to amputations occurring after the first amputation event will be summarised using descriptive statistics (frequency tables with absolute and relative frequencies).

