4.1.2 Secondary Outcomes: Adverse Events Related to Amputation

The term “adverse events related to amputation” is used for events generally known to be related and often preceding amputations. The occurrence of these types of events not necessarily leads to amputation procedures.

[Appendix 6.1](#) contains a list of preferred terms for selecting AEs related to amputation. This list will be reviewed before the conduct of the analysis to ensure that all the PTs are still current in the latest MedDRA version used for the analysis.

This endpoint will be analysed for all patients and for the subset of patients with amputations.

See [Section 4.3.2.2.2](#) for details about the planned analysis.

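### Adverse events preceding amputation are to be compared between empagliflozin and placebo, but only among amputated patients, so the comparison is not randomised and its ratios can mislead

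*SAP*

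**What the plan says.** **Objective.** Protocol section 8 lists as exploratory to "assess the frequencies and incidence rates of patients with AEs related to amputation preceding the amputation for empagliflozin compared with placebo", in both pools and in each study.

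**Population.** Protocol section 9.7.2.1 states that "AEs related to amputation preceding the amputation will be summarised for patients with amputation" and leaves out AEs with onset after the amputation. Table 9.7: 2 of the Protocol places this work under "Patients with amputations only, i.e. preceding events", with frequencies, incidence rates and Kaplan-Meier but no Cox model, for SAF-M1, SAF-M2 and each study. SAP Table 4.3: 1 agrees. SAP section 4.3.2.2.2 asks for the frequency tables by treatment and by group of preferred terms.

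**Parallel analysis.** The AE terms are also the secondary outcome. SAP section 4.1.2 says: "This endpoint will be analysed for all patients and for the subset of patients with amputations". The sentence in SAP section 4.3.2.2.2 likewise names all treated patients first and then adds the analysis "in the subgroup of patients with a subsequent amputation, but for events before the actual amputation only". In all treated patients there are frequencies, incidence rates, Kaplan-Meier and Cox models. Cox models by AE group need at least 14 patients with events over the two arms.

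**Not covered.** No planned table takes all treated patients as denominator for an AE that was followed by an LLA. The limitations in Protocol section 9.9 do not mention that amputees are a selected group.

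**The concern.** The objective is a treatment comparison, but its denominator is the set of patients who had the primary outcome. If empagliflozin changes who is amputated, which is what the meta-analysis asks, then amputees on empagliflozin and amputees on placebo are no longer groups formed by randomisation. A difference between them in preceding AEs mixes the effect on those AEs with the effect on amputation itself.

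The output will be percentages, rates and curves by arm, under an objective worded as a comparison with placebo, in a report that goes to the EMA (Protocol section 12). A reader could take a ratio below 1 for an AE group as protection, or a ratio of 1 as no effect, when neither is so.

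**Working it through.** **1. Inputs from the documents.** Protocol section 9.5 gives 1245.25 as 2345 + 2342 empagliflozin and 2333 placebo (7020), 1245.110 as about 4126 randomised 1:1, and 1245.121 as about 2850 randomised 1:1. The total is 7020 + 4126 + 2850 = 13,996, which reproduces the stated approx. 14 000. By arm:
- Empagliflozin: 4687 + 2063 + 1425 = 8175
- Placebo: 2333 + 2063 + 1425 = 5821

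The plan gives no figure for the amputee-only analysis. It also gives no LLA risk, no share of LLAs by route and no effect on any AE. What follows is assumed and shown as a range. The ratio 1.97 is borrowed as a scenario value from Protocol section 7, where it is the hazard ratio for a related drug.

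**2. What the amputee-only ratio measures.** Let B be an AE group. For frequencies, exactly:

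amputee-only ratio for B = (ratio of LLA preceded by B, over all treated) ÷ (ratio of LLA over all treated)

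The planned ratio is thus the quantity of interest divided by the primary-outcome effect.

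**3. Exclusive routes.** Let a route hold share s of placebo LLAs and have true ratio r, with other routes unaffected. The LLA ratio is D = 1 − s + s·r. The amputee-only ratio is r/D for the affected route and 1/D for the others.

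| r | s | D | affected, r/D | unaffected, 1/D |
|---|---|---|---|---|
| 1.97 | 10% | 1.097 | 1.80 | 0.91 |
| 1.97 | 30% | 1.291 | 1.53 | 0.77 |
| 1.97 | 50% | 1.485 | 1.33 | 0.67 |
| 0.5 | 10% | 0.95 | 0.53 | 1.05 |
| 0.5 | 50% | 0.75 | 0.67 | 1.33 |

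These ratios do not depend on the level of LLA risk. Over all treated patients, the affected route shows r and the others show 1.00. If every route rises by 1.97, then D = 1.97 and every amputee-only ratio is 1.97/1.97 = 1.00.

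**4. Overlapping AEs.** One patient can count in several AE groups, so exclusive routes are a special case. Assume independent AEs A (5% on placebo) and B (8%), the drug doubling A only, and these LLA risks:

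| joint effect | LLA risk: neither / A / B / both | LLA ratio | B, amputee-only | B then LLA, all treated |
|---|---|---|---|---|
| additive | 0.002 / 0.05 / 0.08 / 0.128 | 1.226 | 0.84 | 1.03 |
| multiplicative | 0.002 / 0.02 / 0.03 / 0.3 | 1.310 | 1.00 | 1.31 |
| more than multiplicative | 0.002 / 0.02 / 0.03 / 0.9 | 1.504 | 1.06 | 1.59 |

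First row in full:
- Placebo LLA risk: 0.95·0.92·0.002 + 0.05·0.92·0.05 + 0.95·0.08·0.08 + 0.05·0.08·0.128 = 0.01064
- Placebo risk of B then LLA: 0.08·(0.95·0.08 + 0.05·0.128) = 0.006592
- Empagliflozin (A at 10%): 0.01304 and 0.006784 in the same way
- All treated: 0.006784/0.006592 = 1.03
- Amputee-only: 1.03 ÷ 1.226 = 0.84

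With A halved instead, the amputee-only ratio for B is 1.11, 1.00 and 0.94 in the three rows.

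**5. Incidence rates.** A simulation of 4 million patients per arm over 3 years, with assumed additive hazards and A doubled, gives for B among amputees 0.76 on frequency and 0.66 to 0.69 on incidence rate. Over all treated patients, B then LLA shows 1.03.

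**6. Pooling.** Study 1245.25 supplies 4687/8175 = 57% of empagliflozin patients and 2333/5821 = 40% of placebo patients. Pooled crude counts would therefore mix a study difference into the comparison.

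**The case against.** **The plan already analyses these AEs in all treated patients.** This stands. A reader of the amputee clause alone might infer that no randomised comparison of these AEs exists, and that would be wrong: a drug effect on vascular, diabetic-foot, wound/infection, nervous-system or volume-depletion AEs can be seen there. But SAP section 4.1.2 itself notes that such events need not lead to amputation. That analysis asks whether the drug changes these AEs, not whether it changes amputations that they preceded.

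**The AE groups are not exclusive.** This stands too. Analyses count patients with AEs, and no rule assigns a patient to one group, so group percentages need not add up to 100%. It is tempting to say that an effect on one route must appear as an opposite effect on the others. Step 4 shows that this holds for exclusive or additive routes, vanishes under multiplicative effects and reverses beyond them. What remains is that the direction is not known in advance, so a reader cannot correct for it.

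**A rise in all routes would not be hidden.** Correct for the meta-analysis as a whole. It would show in the primary LLA analysis in all treated patients. For SAF-M2 the reasons leading to LLA are also tabulated. Only the amputee-only table would be silent.

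**The analysis is exploratory and Kaplan-Meier only, and tables show counts.** This limits the weight of the point. A careful reader could divide the planned count by the number treated. The plan does not say to do so, and its stated comparison uses the other denominator.

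**Conclusion.** The concern holds as a mismatch between one exploratory objective and its denominator. The comparison of preceding AEs is made only within a group selected by the primary outcome, so it is not randomised, and the limitations section does not say so.

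Under assumed exclusive routes and a true ratio of 1.97, unaffected routes would read 0.91 to 0.67 and the affected route 1.80 to 1.33, for route shares of 10% to 50%. In the overlapping examples with one AE doubled, the unaffected AE reads 0.84 to 1.06. All of these rest on assumed shares, risks and joint effects. The identity in step 2 does not.

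The documents do not support two stronger readings: that a false opposite effect is certain, or that a harm could escape the meta-analysis. The primary outcome and the all-treated analyses of these AEs are unaffected. This is a cheap improvement, not a flaw in the main result.

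**What to change.** 1. For each AE group in SAP Appendix 6.1, add the outcome of a first LLA preceded by an AE of that group, with all treated patients of the randomised arm as denominator. Give n/N and the rate per 100 patient-years from treatment start to first LLA or censoring, by study and pooled with study taken into account. Base the empagliflozin-versus-placebo comparison on these tables.
2. Keep the amputee-only tables, labelled descriptive and not for treatment comparison.
3. State the selection in Protocol section 9.9.

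Ending time at risk at first LLA matters. Under the general rule in SAP section 4.3, read literally, an amputee without a preceding AE contributes time after the amputation, when no preceding AE can be counted.

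**Cost.** Some wording and one extra set of tables from data already derived; the person-time is that of the planned LLA incidence rate. The percentages will be small, and a patient with AEs from several groups appears in several rows. For the same reason, a raised ratio for one group does not show that the drug acts through it: in step 4, B then LLA reaches 1.03 to 1.59 although only A was changed. A footnote should say so.

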4.3.2.3 Subgroup analyses

Subgroup analyses will be performed for the subgroups displayed in [Table 4.3: 3](#). Subgroup analyses for SAF-M1 and SAF-M2 will be provided for frequency and incidence rate tables, KM analyses and for Cox models. Subgroup analyses will be performed for amputation events as well as for the adverse events related to amputations analysis.

For Cox models for time to first event analysis the following factors will be included in the model: study, treatment, <subgroup>, treatment by <subgroup> interaction.

For time-to-event endpoints, at a minimum, a count of events will be provided, and if sample size is statistically sufficient, i.e. 14 patients with events in total over the 2 treatment groups for each subgroup category, a statistical analysis using the Cox regression model will be performed. If otherwise the affected category is too small (<14 patients with events) a category may be only described descriptively and no inferential analysis is performed, or the category might be pooled with another category if this is justifiable from a scientific perspective.

Table 4.3: 3 Subgroup analyses

Variable	Subgroup Analysis Categories
Sex	Male Female
Race	White Black/African Asian Other
Geographical region	Europe Africa/Middle East North America Latin America Asia Other (if any)
Age (years) categories	Version 1 < 65 65 to < 75 75 to < 85 ≥ 85 or

	< 65
	65 to < 75
	= 75
	In case of low number of events for patients >= 85
Renal function (eGFR) (CKD-Epi) (mL/min/1.73m ²)	<30 30 to < 45 45 to <60 60 to <90 ≥90
Insulin use	Yes/No (Diabetic patients only)
Metformin use	Yes/No (Diabetic patients only)
SU use	Yes/No (Diabetic patients only)
Loop diuretics	Yes/No
Baseline HbA _{1c} (%)	<8.0, >=8.0
Baseline HbA _{1c} (%)	<8.5, >=8.5
Anticoagulant use	Yes/No
Anti-platelet use	Yes/No
Diuretics	Yes/No
Hypertension	Yes/No
Diabetes	T1DM T2DM No Diabetes (Diabetes yes/no if number of events to low)
Peripheral arterial occlusive disease	Yes/No
Diabetic foot at baseline	Yes/No (Diabetic patients only)
Coronary artery disease	Yes/No
Diabetic neuropathy	Yes/No
Diabetic retinopathy	Yes/No (Diabetic patients only)
History of lower limb amputation	Yes/No
Osteomyelitis	Yes/No
Gangrene	Yes/No
Nephropathy	Yes/No
HF at baseline	Yes/No
Smoking status	current smoker ex-smoker never smoked

6 APPENDIX

6.1 LIST OF PREFERRED TERMS FOR PRECEDING/RELATED EVENTS

Vascular AEs

Angiopathy

Arterial bypass operation

Arterial disorder

Arterial graft

Arterial occlusive disease

Arterial stenosis

Arterial stent insertion

Arteriosclerosis

Arterial thrombosis

Arterial therapeutic procedure

Diabetic microangiopathy

Diabetic vascular disorder

Femoral artery occlusion

Iliac artery occlusion

Intermittent claudication

Ischaemic limb pain

Microangiopathy

PAOD Peripheral arterial occlusive disease

Peripheral ischaemia

Peripheral coldness

Peripheral artery stenosis

Peripheral artery restenosis
Peripheral artery occlusion
Peripheral artery thrombosis
Peripheral vascular disorder
Peripheral ischaemia
Peripheral arterial re-occlusion
Peripheral vascular disorder
Poor peripheral circulation
Peripheral artery angioplasty
Peripheral endarterectomy
Peripheral artery bypass
Peripheral artery stent insertion
Spontaneous amputation
Thrombosis

Diabetic foot related AEs

Atherosclerotic gangrene

Bone abscess

Diabetic foot

Diabetic foot infection

Diabetic gangrene

Diabetic neuropathic ulcer

Diabetic ulcer

Dry gangrene

Cellulitis enterococcal

Cellulitis staphylococcal

Cellulitis streptococcal

Cellulitis gangrenous

Extremity necrosis

Gangrene

Infections Cellulitis

Infected skin ulcer

Infected skin ulcer

Ischaemic ulcer

Localised infection

Necrosis ischaemic

Neuropathic ulcer

Osteitis

Osteomyelitis

Osteomyelitis acute

Osteomyelitis bacterial
Osteomyelitis chronic
Osteomyelitis fungal
Osteomyelitis salmonella
Osteonecrosis
Penetrating atherosclerotic ulcer
Post-operative wound infection
Skin erosion
Skin ulcer
Staphylococcal osteomyelitis
Soft tissue infection
Subperiosteal abscess

Wound/Infection

Abscess limb

Burn infection

Impaired healing

Wound

Skin wound

Skin infection

Subcutaneous abscess

Vasculitic ulcer

Wound abscess

Wound complication

Wound dehiscence

Wound infection

Wound infection bacterial

Wound infection fungal

Wound infection staphylococcal

Wound infection pseudomonas

Wound necrosis

Wound sepsis

Wound treatment

Nervous System Disorders

Areflexia

Autonomic neuropathy

Burning sensation

Diabetic neuropathy

Hypoesthesia

Neuropathy peripheral

Paraesthesia

Peripheral sensory neuropathy

Peripheral sensorimotor neuropathy

Sensory disturbance

Volume depletion

Hypovolaemia

Dehydration

6.2 DATA RETRIEVAL FOR LOWER LIMB AMPUTATIONS IN STUDY 1245.25

Data from study 1245.25 were reviewed for cases of amputation of the (part of) lower limb. Only the treated set was considered. The entire period of the patient's participation in the trial, including after a potential study drug permanent interruption, was included for the case retrieval.

Amputations are not considered adverse events (AE) per se (a stand-alone untoward medical occurrence), but a therapeutic procedure for an AE. Therefore they were not expected to be reported as separate AE with diagnosis "Amputation of ..." and MedDRA coded.

Nevertheless, the investigators often reported it in the free-text comment field of the AE leading to the amputation. Being a therapeutic procedure, it was often reported as concomitant therapy as well.

Taking into consideration how amputations were reported, the following search strategy was established:

The adverse events were reviewed for any PT of amputation.

The concomitant treatment was searched for any amputation based on the coded entries. The output included an aggregated table per type of amputation and a line listing.

The treated sets were searched for any mentioning of "amput" (to account for "amputation", "amputed", "amputing" etc.) and "disarticul" (to account for "disarticulation", "disarticulating", "disarticulated" etc.) in the concomitant therapy, adverse event comments, investigators comments or change of antidiabetic background therapy. The output included line-listings.

The narratives (in case of serious adverse event) or line-listings of the adverse events and concomitant therapies of the patients included in these outputs were medically reviewed to confirm / reject the occurrence of LLA (e.g. in case of rectum amputation).

To account for potential cases of amputation not reported as a comment of an event or as concomitant therapy, a medical review of all the narratives (all the narratives were considered, including for the patients who permanently stopped the study drug but remained in the trial) was done, which had a hit in a syntax search. The search included any mentioning of "amput" or "disarticul".

To increase the sensitivity, a search for "resect" (to account for "resection", "resected", "resecting" etc.) or "remov" (to account for "removed", "removal", "removed", "removing" etc.) was also done.

The identification of the confirmed cases of LLA was based on the medical review. Cases included were any amputation/disarticulation of the lower limb, independent of the cause.

The following cases were excluded:

- Amputation/resection/removal of other part of the body than limb (e.g. rectum amputation).
- Amputation of the (part of) upper limb. This is in line with the common medical knowledge that the diabetes mellitus is a risk factor of LLA, not for upper limb.
- Debridement without mentioning of concomitant amputation. It does not include loss of the lower limb segment.
- Necrosectomy without mentioning of concomitant amputation. It does not include loss of the lower limb segment.
- Amputation stump revision without mentioning of an extension of the amputation, and were amputation a preexisting condition at study start.
- Nail removal or resection without mentioning of concomitant amputation. It does not include loss of the lower limb segment.

If the date of the amputation was not properly documented, it was derived by BI based on the available information, i.e. if the date of the procedure was not reported, the date of the admission in the hospital, or the date of the diagnosis for which the amputation was done – whatever occurred later – was used. In one case the day of admission (which was after the date of the diagnosis) was not reported, but only the month and year. It was imputed to 15th in accordance to the imputation done for the CTR.

